4.4 Participants

4.4.1 Inclusion Criteria

Eligible will be male and female patients > 18 years of age.

Eligible will be patients with previous coronary stenting undergoing any kind of surgical or operative endoscopic procedure at the participating Centers, irrespective of the distance in time between stenting and surgery.

Both candidates to elective and urgent/emergent surgical procedures will be included in the MONET registry.

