2. BACKGROUND AND RATIONALE

Every year more than 1 million PCIs are performed in United States and similar numbers in Europe^{1,2}. In more than 85% of cases a coronary stent is implanted³, with the ensuing need for prolonged antiplatelet therapy in order to prevent stent thrombosis (ST). The international Practice Guidelines recommend dual antiplatelet therapy (DAPT) with aspirin and a P2Y₁₂ receptor antagonist for at least one month after bare metal stent (BMS) implantation and for 6 months after drug eluting stent (DES)^{4,5}. In patients with acute coronary syndrome (ACS), DAPT should be prolonged up to 12 months.

Premature discontinuation of antiplatelet therapy is associated with a significant increase in the risk of ST⁶⁻⁹, an infrequent but lifethreatening event which occurs most of the times as acute myocardial infarction (MI), with a mortality rate of 10-40%. The single most important predictor of ST is the cessation of antiplatelet therapy¹⁰⁻¹². Previous studies demonstrated that premature discontinuation of antiplatelet therapy (permanent or transitory) after stent implantation occurs in 10-50% of patients^{7,13}, most frequently due to surgical interventions¹³.

It has been estimated that 4-8% of patients submitted to stent implantation undergo surgery within the first year³. The perioperative management of antiplatelet therapy represents a relevant issue, not only as it is epidemiologically relevant, but also because it may have significant clinical consequences¹⁷. A patient who experiences a perioperative MI has an inhospital mortality of 15-25%¹⁸⁻²⁰.

Perioperative management of antiplatelet therapies raises important challenges and safety concerns. On one hand, withholding therapy to reduce the risk of bleeding complications is associated with a heightened risk of ischemic events, including life-threatening stent thrombosis (ST), myocardial infarction (MI) and stroke [8-10]. Surgery leads to inflammatory, hypercoagulable and hypoxic states which are associated with plaque instability and perioperative

arterial thrombosis^{3,14}. Thus, the perioperative risk of ST and other cardiac ischemic events is high, particularly if antiplatelet therapy is discontinued^{15,16}. On the other hand, maintaining antithrombotic therapy may increase the risk of bleeding and the need for transfusions, which are both known determinants of poor prognosis [3-10].

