4.2 Primary endpoint

- Rate of discontinuation of P2Y12 inhibitors and/or aspirin (without bridging) in the first 3 months after PCI with low risk characteristics and 6 months after PCI with high risk characteristics or any antiplatelet therapy discontinuation without bridging therapy

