4.4.2 Exclusion criteria

Unwillingness/inability to sign the Informed Consent Form (ICF). Patients with an active bleeding requiring discontinuation of one or both antiplatelet agents will be also excluded. There are no other exclusion criteria.

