6. DEFINITIONS OF THE ENDPOINT COMPONENTS

6.1 Antiplatelet therapy discontinuation

Antiplatelet discontinuation is defined as P2Y₁₂ inhibitors and/or aspirin withdrawal for >5 days at the time of surgical procedure without bridging therapy with antiplatelet agents in the first 3 months after PCI with low risk characteristics and 6 months after PCI with high risk characteristics or any any antiplatelet therapy discontinuation without bridging therapy at any time after PCI. A detailed description on the perioperative management of oral antiplatelet therapy will be obtained for both aspirin and P2Y₁₂ inhibitors (ticlopidine, clopidogrel, prasugrel, and ticagrelor). This includes the time delay from drug interruption to surgery as well as the time from surgery to reintroduction of therapy. The use of any bridging strategy will also be recorded. According to the SAS 2 Consensus Document, in selected patients at high risk for both bleeding and ischemic events, when withdrawal of oral antiplatelet therapy is required, bridging with cangrelor or with a short-acting intravenous glycoprotein IIb/IIIa inhibitor (GPI) (tirofiban or eptifibatide) can be considered.

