7. STATISTICS

7.1 The Number of Participants

Consecutive patients will be enrolled over one year of time at the participating Centers.

Cases and controls patients will be divided into those who will use Consensus Document “Stent and Surgery-2” (group 1) vs those who traditionally will be managed by local practice (group 2). On the basis of previous data reported SAS, a sample size of 1623 patients would be required to have a case-control matching 1:2, assuming a study power of 80% and 5% significance. Of those, 324 case-patients (20% of group 1) vs 162 control-patients (ratio 1:2) would be required for enrollment within one-year after implanted stents. Two preplanned interim analyses will be performed by an independent statistician when 800 and 1500 of patients will be enrolled.

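### The primary discontinuation rate has no at-risk set, so it mixes who was on antiplatelet therapy with how therapy was managed around surgery

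*Combined protocol and SAP*

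**What the plan says.** **Who enters.** Section 4.4.1 requires adulthood, a previous coronary stent and a procedure, "irrespective of the distance in time between stenting and surgery". Section 4.4.2 excludes patients without consent and says "Patients with an active bleeding requiring discontinuation of one or both antiplatelet agents will be also excluded". It then closes the list: "There are no other exclusion criteria". Current antiplatelet use is not required anywhere.

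**What is counted.** Section 4.2 names the primary endpoint as "Rate of discontinuation of P2Y12 inhibitors and/or aspirin (without bridging) in the first 3 months after PCI with low risk characteristics", with a 6-month window for high-risk PCI and a second limb for any unbridged discontinuation. Section 6.1 defines the first limb as P2Y12 "inhibitors and/or aspirin withdrawal for >5 days at the time of surgical procedure without bridging therapy with antiplatelet agents" within those windows. Its second limb covers any "antiplatelet therapy discontinuation without bridging therapy at any time after PCI". Neither section states a denominator, a date on which the patient must have been on the drug, or how a course completed as planned is scored.

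**How long therapy is expected to last.** Section 2 gives dual therapy a finite course: at least one month after a bare metal stent, 6 months after a drug-eluting stent, and longer in one setting: "In patients with acute coronary syndrome (ACS), DAPT should be prolonged up to 12 months".

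**How groups are compared.** Groups follow centre practice (Sections 4.1 and 7.1). Section 7.2 plans 1:2 propensity matching, lists no covariates, and selects them by backward elimination at 0.05.

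**The concern.** A rate of stopping a drug is interpretable only among people who were taking it. Here a patient several years after PCI, long since off the P2Y12 inhibitor as planned, is eligible. Two analysts could score that patient in opposite ways:

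- **As an event.** Read literally, the second limb of 6.1 counts any unbridged discontinuation after PCI, with no minimum duration and no link to the operation. The first limb has a minimum of more than 5 days but no maximum.
- **As a certain non-event.** A patient not on the drug cannot stop it, but nothing removes that patient from the denominator.

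Either way the rate depends on the share of patients on therapy. If that share differs between the two sets of centres, the primary comparison can show a difference when perioperative handling is the same. Even when the share is equal, off-drug patients dilute a real difference.

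**Working it through.** **1. The plan's own figure.** The sample size of 1623 in Section 7.1 cannot be reproduced, because no event rates or effect size are given. At 80% power and two-sided 5%, 541:1,082 fits 30% vs 23.5%, among many other pairs. The total therefore says nothing about the expected rate or the share on therapy. The 541:1,082 split is my assumption: 1623 / 3 = 541, using the stated 1:2 ratio.

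**2. Inputs.** The documents give neither of these, so both are assumed:
- f = share on therapy before surgery
- d = share of those on therapy who stop, unbridged, for surgery

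**3. Formulas.**
- Off-drug patients counted as events: rate = (1 − f) + f × d
- Off-drug patients kept as non-events: rate = f × d
- At-risk denominator: rate = d, whatever f is

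**4. Effect on the rate, d = 30%.** The last column lets d run from 50% down to 10%.

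| f | Off-drug = event | Off-drug = non-event | At-risk set | Share of events that are only off-drug |
|---|---|---|---|---|
| 20% | 86% | 6% | 30% | 89–98% |
| 50% | 65% | 15% | 30% | 67–91% |
| 80% | 44% | 24% | 30% | 33–71% |
| 95% | 33.5% | 28.5% | 30% | 10–34% |

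The last column applies to the event scoring and is (1 − f) / [(1 − f) + f × d].

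**5. False difference with identical management (d = 30% in both groups).** The smaller group is given the lower f; the size of the difference does not depend on that choice.

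| f, 541 vs 1,082 | Scoring | Rates | Difference | Chance of p < 0.05 |
|---|---|---|---|---|
| 70% vs 80% | event | 51% vs 44% | 7 points | 76% |
| 70% vs 80% | non-event | 21% vs 24% | 3 points | 27% |
| 90% vs 95% | event | 37% vs 33.5% | 3.5 points | 29% |
| 90% vs 95% | non-event | 27% vs 28.5% | 1.5 points | 9% |

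First row in full: 0.30 + 0.70 × 0.30 = 0.51 and 0.20 + 0.80 × 0.30 = 0.44. The pooled rate is (541 × 0.51 + 1,082 × 0.44) / 1623 = 0.463. The standard error is √[0.463 × 0.537 × (1/541 + 1/1,082)] = 0.0263, and z = 0.07 / 0.0263 = 2.67. The two scorings also push the difference in opposite directions.

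**6. Dilution of a real difference.** Take d = 30% vs 20% and the same f in both groups. With f = 50%, power at 541:1,082 is 50% if off-drug patients are events and 83% if they are non-events. It is 88% if only the on-therapy half is analysed. When everyone is on therapy it is 99%.

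**The case against.** **In context, discontinuation means perioperative interruption.** Section 6.1 goes on to describe perioperative management and the delay from interruption to surgery, and Section 4.5.3 records perioperative stop and restart dates. This is the more natural intent, and it makes the event scoring the less likely one. But it is not written as a rule, and adopting it leads only to the other scoring: off-drug patients remain as certain non-events. The distortion shrinks (3 or 1.5 points in the examples) but does not vanish.

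**Most patients will be on aspirin.** The endpoint covers either drug, and Section 2 says most procedures can be done on aspirin. This point largely stands for the non-event scoring, where aspirin users can still have an event. It helps less under the event scoring, where an aspirin user who finished a P2Y12 course still counts. An example built on P2Y12 users alone would look starker but would not represent the endpoint as defined.

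**The 3- and 6-month windows protect the endpoint.** They do for the first limb, where most patients should still be on therapy. The second limb has no window.

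**Matching deals with it.** The date of latest stenting and medications are captured, so adjustment is possible. With covariates unlisted and subject to elimination, balance is not assured, and matching cannot decide how an off-drug patient is scored.

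**Stronger readings that the documents do not support.**
- A reader might infer from "324 case-patients (20% of group 1" that about 80% of patients will be more than a year from stenting. The sentence is too garbled for that: 0.20 × 1623 = 324.6, so 324 looks like 20% of the total, and 324 to 162 is 2:1.
- A reader might say that the consensus document has no influence on therapy status at entry. Its full text is not in the material reviewed, and the summary in Section 2 does advise on timing of surgery after PCI, which affects who is still on therapy.

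**Conclusion.** The defect is real: the primary endpoint has no at-risk set, and the same data can yield very different rates depending on an unstated scoring choice. Because groups are formed by centre, with no assured balance on baseline therapy or time since PCI, the comparison can be biased or diluted.

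Its size is not known. A reader might infer that the rate mostly reflects who was still on therapy, or that completed courses would make up most events. The documents do not give the share on therapy, so neither can be claimed. The effect is likely to be greater for P2Y12 inhibitors late after PCI, and smaller for aspirin or inside the 3- and 6-month windows. On the assumed inputs, the false difference runs from 1.5 to 7 points with identical management. All of these figures rest on the assumed f, d and 541:1,082 split. The missing at-risk set does not depend on them.

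**What to change.** In Sections 4.2, 6.1 and 7.2:

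- Define an at-risk set separately for aspirin and for P2Y12 inhibitors. It contains patients taking the drug at the preoperative evaluation, plus those whose recorded stop before that date was made because of the planned procedure. Without the second group, patients who had already stopped for surgery when screened (Section 4.5.2) would be lost, and they are true events.
- Count an event only when a drug in that set is interrupted, unbridged, for the index procedure. State that planned completion of dual therapy unrelated to the procedure is not an event.
- Report the rate for each drug, and say which rate, or which combination of the two, is the primary comparison.
- Force baseline antiplatelet therapy and time since PCI into the propensity model, exempt from backward elimination.
- Keep patients on no antiplatelet drug in the registry for the 30-day clinical endpoints, outside the primary rate.

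**Cost.** Mostly wording: medications at screening and perioperative stop and restart dates are already collected (Section 4.5.3, Appendix A). The eCRF needs one further item, the reason for any stop before the preoperative evaluation. The denominator for the primary rate becomes smaller, so the sample size should be checked against it. No change to clinical management is implied.

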4.4.2 Exclusion criteria

Unwillingness/inability to sign the Informed Consent Form (ICF). Patients with an active bleeding requiring discontinuation of one or both antiplatelet agents will be also excluded. There are no other exclusion criteria.

4.4.3 Enrolment time

The enrolment period is 12 months after authorization of respective Ethics Committee.

4.5 Study Procedures

4.5.1 Informed Consent

Patients will be asked to sign an ICF for participation in the Registry.

4.5.2 Screening

Screening for inclusion into the registry will be made at the time of preoperative evaluation: this will be made by the consultant cardiologist in cooperation with the anaesthesiologist and/or surgeon/endoscopist in charge of the operation.

4.5.3 In-hospital assessments

The MONET registry does not imply any assessments additional to routine treatment. The following clinical and laboratory variables will be captured by the eCRF:

Clinical characteristics

- Age, gender, body weight.
- Selected coronary risk factors, such as diabetic status, smoking, hypertension, dyslipidemia.

- Cardiovascular status: prior MI, PCI (date of latest stenting), CABG, heart failure, atrial fibrillation, latest left ventricular ejection fraction.

Laboratory tests

- Baseline serum creatinine (eGFR will be automatically calculated by the eCRF using the Cockcroft-Gault formula) and peak serum creatinine during hospital stay.
- Baseline haemoglobin/haematocrit and nadir values during hospital stay.
- CKMB and troponin values should be checked at 6-hour intervals for 24 hours after any suspect ischemic symptoms and/or ischemic ECG changes in the perioperative period, unless otherwise recommended by local practice. The peak value of CKMB will be recorded in the eCRF.

Electrocardiogram

A standard 12-lead ECG will be taken preoperatively, in the case of ischemic symptoms and at discharge.

Concomitant Medications

The following medications will be captured by the eCRF:

- Aspirin
- P2Y₁₂ inhibitors (further subdivided as ticlopidine, clopidogrel, prasugrel, ticagrelor)
- Betablockers
- Statins
- ACEI, ARBS
- Oral anticoagulants (warfarin, acenocumarol, apixaban, dabigatran, edoxaban, rivaroxaban)

- Low-molecular weight heparin
- Tirofiban or eptifibatide
- Cangrelor

The dates and times of perioperative discontinuation and reinstitution (if any) will also be captured.

Drug therapy at discharge and at the 30-day contact will be captured by the eCRF.

Index PCI and surgical procedure details

Details of PCI and surgical procedures will be obtained from interrogation of the medical records and hospital charts.

The delay from stenting to surgery and the type of stent (BMS, first or second generation DES), stent number, length and diameter will be recorded. Surgeries will risk-stratified according to the American College of Cardiology/American Heart Association classification [11]. Moreover, the American Society of Anaesthesiologists (ASA) physical status will be assessed for each patient [21].

For each patient, surgical hemorrhagic and thrombotic risk (according to the SAS 2 Consensus Document definitions) will be identified at the time of data analysis according to clinical and angiographic characteristics that will be captured in the eCRF.

Outcome Events

The following outcome events will be captured by the eCRF:

- Death

- Myocardial infarction, recurrent ischemia, heart failure, ventricular tachycardia, ventricular fibrillation.
- Major bleeding
- Transfusions
- Reoperation due to bleeding

See point 8 for definitions

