3.2 Secondary Objectives

- To assess ischemic and hemorrhagic events in relation to the application of the Consensus Document. Length of any antiplatelet discontinuation and delay in performing surgical procedures will also be evaluated.

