4.3 Secondary endpoints

Patients undergoing non cardiac surgery:

- The composite of death, myocardial infarction, probable/definite stent thrombosis according the Academic Research Consortium definition⁴⁴ and bleeding events of Bleeding Academic Research Consortium (BARC) grade ≥ 3 at 30 days
- The composite of death, myocardial infarction and probable/definite stent at 30 days
- The incidence of bleeding events of Bleeding Academic Research Consortium (BARC) grade ≥ 3 at 30 days
- The type and the length of discontinuation of any antiplatelet therapy in patients undergoing non cardiac surgery according to time from PCI to surgery
- Rate of non cardiac surgical procedures within 12 months from PCI divided into quartiles (0-3, 3-6, 6-9, 9-12 months)
- Delay in performing non cardiac surgical procedure

Patients undergoing cardiac surgery:

- The composite of death, myocardial infarction, probable/definite stent thrombosis according the Academic Research Consortium definition⁴⁴ and bleeding events of Bleeding Academic Research Consortium (BARC) grade ≥ 4 at 30 days
- The composite of death, myocardial infarction and probable/definite stent at 30 days
- The incidence of bleeding events of Bleeding Academic Research Consortium (BARC) grade ≥ 4 at 30 days
- The type and the length of discontinuation of any antiplatelet therapy in patients undergoing cardiac surgery according to time from PCI to surgery
- Rate of cardiac surgical procedures within 12 months from PCI divided into quartiles (0-3, 3-6, 6-9, 9-12 months)
- Delay in performing cardiac surgical procedure

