7.2 Description of Statistical Methods

Continuous numeric variables will report as means with SD and compared using the Student’s t- or Wilcoxon rank-sum test. Categorical variables will be presented as counts and percentages and will be compared using the chi-square or Fisher’s exact test. To examine the effect of significant factors on two different groups (Group 1 vs Group 2) the hazard ratio of the interaction term will be calculated. To identify the independent predictors for in hospital NACE, 30day MACE and 30-day BARC bleedings, first univariate and then multivariate logistic regression models will apply. The BARC bleedings will be considered according to type of surgery. Specifically, BARC bleedings grade ≥ 3 will be considered in patients undergoing cardiac surgery, and BARC bleedings grade ≥ 4 will be taken into account for non-cardiac surgery. Covariates for multivariable models will be selected on the basis of a backward stepwise algorithm in a Cox proportional hazards model. Additionally, to minimise group differences on confounding covariates between patients who will be managed with consensus document (group 1) and those who will be received local practice (group 2), a 1:2 propensity score matching would be used. Propensity scores will be calculated with logistic regression, with multiple imputation and backwards elimination with a significance level to stay of 0.05. To ensure that the comparison between two groups (group 1 vs group 2) would not be bias, the proportion of patients who will not received consensus document within center that traditionally used it, will be excluded. The results will be presented as ORs with 95% confidence intervals (CI) and p values. For all

analyses, a two-sided $P <0.05$ will be required for statistical significance. All data will be analyzed using the Statistical Package of Social Sciences version 20 (IBM SPSS, Chicago, IL).

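### Length of antiplatelet discontinuation is measured to restart, but the plan has no method for patients who have not restarted by the 30-day contact or who die first

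*Combined protocol and SAP*

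**What the plan says.** Section 3.2 makes length a secondary objective: "Length of any antiplatelet discontinuation and delay in performing surgical procedures will also be evaluated". Section 4.3 lists it as a secondary endpoint, "The type and the length of discontinuation of any antiplatelet therapy in patients undergoing non cardiac surgery according to time from PCI to surgery", with a parallel item for cardiac surgery.

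Section 6.1 gives the two parts of the interval: "This includes the time delay from drug interruption to surgery as well as the time from surgery to reintroduction of therapy". Section 4.5.3 collects the dates: "The dates and times of perioperative discontinuation and reinstitution (if any) will also be captured". It goes on: "Drug therapy at discharge and at the 30-day contact will be captured by the eCRF". Section 4.5.4 sets the last planned contact at 30 days after surgery, with 7 days either side, and asks for ongoing medications there.

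For analysis, section 7.2 says: "Continuous numeric variables will report as means with SD and compared using the Student’s t- or Wilcoxon rank-sum test". Time-to-event terms do appear in 7.2 (a hazard ratio for an interaction term, and a Cox model for choosing covariates), but neither is tied to length of discontinuation. Multiple imputation is named only for the propensity score. No section says how length is obtained when there is no restart date.

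**The concern.** A t-test or Wilcoxon test needs a number for every patient. The post-operative part of the interval ends at restart, so two kinds of patient have no number. One is still off the drug at the last contact, where the length is known only to exceed the time observed. The other died before restarting, where the length was cut off and has no restart to run to.

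Applied literally, the stated method leaves both with a missing value. Each way of filling the gap gives a different answer:

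- Omission removes the longest observed interruptions.
- Counting to the contact understates them, and makes the value depend on whether the contact fell on day 23 or day 37.
- Counting to death turns an early death into a short interruption, as if therapy had been restarted promptly.

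The comparison is between non-randomised groups of centres, and SAS 2 itself addresses post-operative resumption (section 2). The share not restarted could therefore differ between groups. A rule chosen after the data are seen could change the reported contrast.

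**Working it through.** The plan gives no figure for length of discontinuation, so there is none to reproduce. The sample size in section 7.1 is not linked to this endpoint. The check is therefore an illustration, and all its inputs are assumptions.

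**Inputs (assumed)**
- 5 days off the drug before surgery, for every patient.
- Among patients who restart before day 30, the time from surgery to restart is exponential with mean 3 or 7 days, truncated at day 30.
- A share f has not restarted by day 30: 0%, 2%, 5%, 10% or 20%.

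**Step 1: mean length in restarters only.** Simulation gives 7.99 days (mean 3) and 11.57 days (mean 7). The closed form 5 + m − 30/(e^(30/m) − 1) gives 8.00 and 11.58, which agrees.

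**Step 2: lower-bound mean with everyone kept.** A non-restarter has been off therapy for at least 5 + 30 = 35 days, so

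lower bound = (1 − f) × restarter mean + f × 35.

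At f = 10%, for example: 0.90 × 7.99 + 0.10 × 35 = 10.69, and 0.90 × 11.57 + 0.10 × 35 = 13.91.

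**Step 3: understatement if non-restarters are omitted** = 1 − restarter mean / lower bound.

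| f | Lower bound, mean 3 | Understated by at least | Lower bound, mean 7 | Understated by at least |
|---|---|---|---|---|
| 0% | 7.99 | 0% | 11.57 | 0% |
| 2% | 8.53 | 6% | 12.04 | 4% |
| 5% | 9.34 | 14% | 12.74 | 9% |
| 10% | 10.69 | 25% | 13.91 | 17% |
| 20% | 13.39 | 40% | 16.26 | 29% |

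These are minimum figures because the true length of a non-restarter exceeds 35 days. For the same reason the lower-bound column, which is what counting to day 30 would report, is itself too low.

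**Step 4: dependence on the date of the contact.** If non-restarters are counted to the contact, moving it from day 23 to day 37 changes each of their values by 14 days. At f = 10% that moves the group mean by 0.10 × 14 = 1.4 days with no change in treatment.

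**Step 5: the median.** At f = 10% it moves from 7.07 to 7.43 days (mean 3) or from 9.76 to 10.56 (mean 7). The median is much less sensitive, but section 7.2 reports means.

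Deaths before restart are not in this illustration. For them the difficulty is that no length is defined, and the direction of any error depends on how they are handled.

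**The case against.** The strongest reply is that the plan is silent, and silence is not a rule to exclude. This stands. A reader might infer that the longest interruptions will drop out, but no section prescribes an analysis of restarters only. The understatement is conditional on how the gap is filled.

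A second reply is that the needed data are already planned. This also stands. A reader might infer that a group of centres with many permanent stops could look the same as one that restarts nearly everyone. The documents do not support that: drug therapy at discharge and at 30 days is captured, so the share off therapy is available by group. The endpoint also covers the type of discontinuation, which is undefined but could separate permanent from temporary stops. The gap lies in the analysis rule, not in data capture.

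Third, a reader might infer that the patients without a restart date are those at highest risk. Section 2 links stopping therapy to stent thrombosis but gives no risk by length of interruption. Section 4.4.1 enrols patients at any distance from stenting, and section 2 describes dual therapy as time-limited. Some non-restarts may therefore be planned ends of treatment.

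Fourth, the share not restarted is unknown and could be small, so the effect could be negligible.

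What these replies do not supply is a value for an unfinished interval. The stated tests still cannot be applied to it without a further rule.

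**Conclusion.** The point holds as a gap in the analysis of one secondary endpoint, reported for both surgery groups. Length is defined to restart, the plan foresees patients with no restart, and section 7.2 has no method for lengths that are censored or cut off by death. If patients still off therapy at the contact are omitted, or counted only to the contact, mean length is understated whenever there are any such patients.

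Under the assumed restart times the omission bias is at least about 4-6% at 2% not restarted and 17-25% at 10%, and zero if everyone restarts. These percentages rest wholly on assumptions about pre-operative days, restart times and the share not restarted. They illustrate the size and do not predict what the registry would report.

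The primary endpoint is a rate of discontinuation and needs no restart date. The 30-day clinical composites do not use length. The change should be made, but the main conclusions do not depend on it.

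**What to change.** In sections 4.3 and 7.2, define the endpoint as time from stop to restart, separately for aspirin and P2Y12 inhibitor. Censor patients not restarted at the date of the 30-day contact, and treat death before restart as a competing event. Keep the planned breakdown by time from PCI to surgery.

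Report by group the cumulative proportion restarted and the proportion still off therapy at the contact, using the 30-day drug status already collected. Show intended permanent stops separately from patients who have not yet restarted.

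Other rules, such as a worst-rank Wilcoxon test, or length among restarters shown beside the proportion still off therapy, would also close the gap if fixed in advance. The time-to-restart analysis is preferred because it uses the observed time off therapy for every patient who stopped.

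The cost is a few sentences in the plan, slightly more analysis work and, if it is not already there, one eCRF response option distinguishing an intended permanent stop from not yet restarted. No additional contact is needed.
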